12.3. Data Analyses

Presentation of summary statistics for continuous variables will include N, mean, median, standard deviation, minimum, and maximum values for non-missing data. For categorical variables, the number and percentage under each category for non-missing data will be presented.

Additionally, subjects meeting this study's eligibility criteria under the PFD Registry may be included in the analyses plan. The intention is to utilize a shared control arm from the PFD Registry.

12.3.1. Rate of Office-Based Intervention for Recurrence

Statistical testing will be performed to determine if the rate of office-based intervention for recurrence in the treatment group will be superior to the control group. The null hypothesis is that the rate of office-based intervention for recurrence in treatment group is greater than or equal to the rate in control group:

$$H_0: \pi_{treatment} - \pi_{control} \geq 0$$

The alternative hypothesis is:

$$H_a: \pi_{treatment} - \pi_{control} < 0$$

where $\pi_{treatment}$ and $\pi_{control}$ are the office-based intervention rates for recurrence in treatment group and control group respectively. The rejection of null hypothesis indicates the superiority of the treatment group over the control group.

12.3.2. Rate of Surgical Intervention for Recurrence

Statistical testing will be performed to determine if the rate of surgical intervention for recurrence in treatment group will be superior to the control group. The null hypothesis is that the rate of surgical intervention for recurrence in treatment group is greater than or equal to the rate in control group:

$$H_0: \pi_{treatment} - \pi_{control} \geq 0$$

The alternative hypothesis is:

$$H_a: \pi_{treatment} - \pi_{control} < 0$$

where $\pi_{treatment}$ and $\pi_{control}$ are the surgical intervention rates for recurrence in treatment group and control group respectively. The rejection of null hypothesis indicates the superiority of the treatment group over the control group.

The propensity score adjusted analysis described in Section 12.2.3 (Propensity Score Methodology) will be used for testing the null hypothesis and computing the confidence intervals for rate of office-based intervention for recurrence and surgical intervention for recurrence between treatment group and control group.

12.3.3. Rate of Office-Based Intervention for Complications

Statistical testing will be performed to determine if the rate of office-based intervention for complications in the mesh (treatment) group is non-inferior to the native tissue repair (control) group. The null hypothesis is that the rate of office-based intervention for complications in treatment group is greater than or equal to the rate in control group plus margin:

$$H_0: \pi_{treatment} - \pi_{control} \geq \Delta$$

The alternative hypothesis is:

$$H_a: \pi_{treatment} - \pi_{control} < \Delta$$

where $\pi_{treatment}$ and $\pi_{control}$ are the office-based intervention rates for complication in treatment group and control group respectively, and $\Delta > 0$ is defined as the non-inferiority margin.

The rate of office-based intervention for complication is anticipated to be approximately 2%. With type I error of 0.025 and type II error of 0.10 (power 90%), 330 subjects (165 subjects per arm) are needed to detect non-inferiority with a margin of 5%.

12.3.4. Rate of Surgical Intervention for Complications

Statistical testing will be performed to determine if the rate of surgical intervention for complications of the mesh (treatment) group is non-inferior to the native tissue repair (control) group. The null hypothesis is that the rate of surgical intervention for complications in treatment group is greater than or equal to the rate in control group plus margin:

$$H_0: \pi_{treatment} - \pi_{control} \geq \Delta$$

The alternative hypothesis is:

$$H_a: \pi_{treatment} - \pi_{control} < \Delta$$

where $\pi_{treatment}$ and $\pi_{control}$ are the probabilities of having surgical intervention for complication in treatment group and control group respectively, and $\Delta > 0$ is defined as the non-inferiority margin.

The rate of surgical intervention complication is anticipated to be approximately 1%. With type I error of 0.025 and type II error of 0.10 (power 90%), 260 subjects (130 subjects per arm) are needed to detect non-inferiority with a margin of 4%.

The propensity score adjusted analysis described in Section 12.2.3 (Propensity Score Methodology) will be used for testing the null hypothesis and computing the confidence intervals for rate office-based intervention for complication and surgical intervention for complication between treatment group and control group.

For each group, logistic regression will be performed, to include office-based intervention for recurrence as a covariate for analyzing the primary endpoint (success rate of improvement in pelvic organ prolapse at 36 months) data.

For each group, Cox regression will be performed, to include surgical intervention for recurrent prolapse as a covariate for analyzing adverse events (pelvic pain, infection, vaginal shortening, vaginal scarring, de novo vaginal bleeding, fistula formation and/or de novo voiding dysfunction) data.

Descriptive statistics for the baseline characteristics and QOL outcome for the non-surgery (i.e. pessary) group will be summarized from the AUGS PFD Registry Level 1/2 database.

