12.1.1.2. Sample Size

The statistical power calculation is based on a superiority assumption with a binary primary outcome. Success, based on a composite endpoint of anatomic and symptomatic success at 36 month is assumed to be 70.0% for the native tissue arm and 85.0% for transvaginal mesh arm.¹⁷⁻²¹ With 2-sided type I error of 0.05 and type II error of 0.1 (power 90%), 316 subjects (158 subjects per arm) are needed to detect 15% difference of transvaginal mesh to native tissue repair. In addition to a superiority assumption, statistical testing will be performed for non-inferiority using a margin of -12%.

To assess for safety, the overall complication rate (i.e. serious adverse device effects and serious procedure-related adverse events) is anticipated to be approximately 14%.²² With type I error of 0.05 and type II error of 0.20 (power 80%), 298 subjects (149 subjects per arm) are needed to detect non-inferiority with a margin of 10%.

To assess for office-based interventions for complications, the rate is anticipated to be approximately 2%.²² With type I error of 0.025 and type II error of 0.10 (power 90%), 330 subjects (165 subjects per arm) are needed to detect non-inferiority with a margin of 5%.

To assess for of surgical intervention for complications, the rate is anticipated to be approximately 1%.²² With type I error of 0.025 and type II error of 0.10 (power 90%), 260 subjects (130 subjects per arm) are needed to detect non-inferiority with a margin of 4%.

Non-surgical subjects will be enrolled by the PFD Registry and analyzed in this clinical study. Non-surgical subjects will not be enrolled into this clinical study. Using the above calculations and assuming a 20% loss to follow-up rate, a total of 414 subjects (207 per study arm) will be enrolled to achieve the primary endpoint of success at 36 months.

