12.1.1.3. Statistical Methods

For the primary efficacy endpoint, the comparisons of mesh repair to native tissue repair will be based on a two-sided 95% confidence interval for the treatment difference (mesh minus native tissue repair). If the entire confidence interval is above zero, superiority of mesh repair to native tissue repair will be demonstrated. The confidence interval will be calculated based on the pooling of treatment differences across propensity score strata for a binary endpoint, as described in Section 12.2.3 (Propensity Score Methodology).

If any data on the primary efficacy endpoint is missing, multiple imputation will be performed in which the missing values will be imputed five times under a logistic distribution model, using a fully conditional specification that includes the treatment arm and the assessments of the treatment success endpoint at each of 2, 6, 12, 18, and 24 months. As a sensitivity analysis, the comparison of treatments will also be performed using the following methods:

- Tipping point analysis
- Available cases only (i.e., only the subjects for whom the endpoint was assessed)

For the primary safety endpoint, the proportions will be calculated using for the numerator the number of subjects with an endpoint event and for the denominator the number of subjects in the analysis population (ITT and per protocol group). Non-inferiority will be evaluated using a two-sided 90% confidence interval for the treatment difference (mesh minus native tissue repair). If the entire confidence interval is below the margin (10%), non-inferiority will be demonstrated. The confidence interval will be calculated based on the pooling of treatment differences across propensity score strata for a binary endpoint, as described in Section 12.2.3 (Propensity Score Methodology).

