12.2.3. Propensity Score Methodology

Analyses comparing the treatment groups will be adjusted for the propensity score. The propensity score is the probability that the subject enrolled in the mesh arm rather than the native tissue (control) arm, given the characteristics of the subject and center. The characteristics identified are as follows: age, race, body mass index, smoking, diabetes, post-menopausal, prior prolapse repair, prior hysterectomy, estrogen use, POP-Q C measurement, POP-Q Ba measurement, POP-Q Bp measurement, concomitant repair for stress urinary incontinence, and surgeon case volume. Logistic regression of both treatment arms (i.e., (transvaginal mesh repair vs. native tissue repair) on these characteristics will be used to estimate the propensity score. The subjects will then be partitioned into five strata

corresponding to quintiles of the propensity score. If the balance between treatment arms within the strata is deemed adequate, the treatment difference adjusted for propensity score stratum will be estimated as described in the following.

The propensity adjusted treatment difference will be based on averaging the treatment differences of the propensity score strata. For a binary outcome, the within-stratum treatment difference is $D_j = p_{Tj} - p_{Cj}$, where p_{Tj} and p_{Cj} is the proportion of treatment and control subjects, respectively, in stratum j . The variance of D_j is approximately

$$V_j = \frac{p_{Tj}(1 - p_{Tj})}{n_{Tj}} + \frac{p_{Cj}(1 - p_{Cj})}{n_{Cj}}$$

Denoting the number of subjects in stratum j by $n_j = n_{Tj} + n_{Cj}$, the treatment difference will be estimated by the (weighted) mean of the within-stratum treatment differences

$$D = \sum_j \frac{n_j}{n} D_j$$

where $n = \sum_j n_j$ is the total sample size across all strata and study arms. D is approximately normally distributed with variance

$$V = \sum_j \left(\frac{n_j}{n}\right)^2 V_j$$

from which a confidence interval for the true treatment difference will be constructed. For each continuous outcome, the confidence interval will be constructed similarly, with D and V obtained as above with the treatment difference within each stratum replaced by $D_j = \bar{X}_{Tj} - \bar{X}_{Cj}$, where \bar{X}_{Tj} and \bar{X}_{Cj} , respectively, is the mean of the treatment and control subjects, and

$$V_j = \frac{S_{Tj}^2}{n_{Tj}} + \frac{S_{Cj}^2}{n_{Cj}}$$

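### The unpooled normal interval of Section 12.2.3 is too liberal for the two complication re-intervention tests at 1–2%: false non-inferiority is about 1.4 to 2.2 times the planned 2.5%

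*Combined protocol and SAP*

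**What the plan says.** Section 12.3.3 sets a non-inferiority test for office-based intervention for complications, with an anticipated rate of 2% and a margin of 5%: "With type I error of 0.025 and type II error of 0.10 (power 90%), 330 subjects (165 subjects per arm". Section 12.3.4 does the same for surgical intervention, at 1% with a margin of 4%: "With type I error of 0.025 and type II error of 0.10 (power 90%), 260 subjects (130 subjects per arm". Section 12.1.1.2 repeats both sample sizes.

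Section 12.3.4 then assigns one method to both tests: "Propensity Score Methodology) will be used for testing the null hypothesis and computing the confidence intervals for rate office-based intervention for complication", and the sentence goes on to cover surgical intervention.

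Section 12.2.3 splits subjects into five propensity quintiles. In each stratum it takes the difference in observed proportions, with variance equal to the sum over arms of observed p(1−p)/n. It weights strata by their share of all subjects and treats the weighted difference as approximately normal, "from which a confidence interval for the true treatment difference will be constructed". It gives no confidence level and no alternative for low counts. Levels appear only for other analyses. Section 12.1.1.3 uses 95% for primary efficacy, and for primary safety it says "Non-inferiority will be evaluated using a two-sided 90% confidence interval for the treatment difference". Section 12.3.8 uses 95% for the interim description and Section 12.3.8.2 uses 90% for the interim tests.

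**The concern.** At event rates of 1–2% and 165 to 207 subjects per arm, only a few events are expected in each arm, and many strata will have none. An arm or stratum with no events contributes zero to the Section 12.2.3 variance. The interval is therefore narrowest when few events happen to be seen, which is also when the difference looks most favourable. The upper limit then drops below the margin too easily.

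The error runs in the unsafe direction: mesh could be declared non-inferior for re-intervention for complications when its true excess equals the margin, and this would happen more often than the stated 2.5%. The stated 90% power relies on the same variance, so it would not survive a method that holds its level.

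**Working it through.** **Inputs.** Control rates 2% and 1%, margins 5% and 4%, type I error 0.025 and power 90% (Sections 12.3.3, 12.3.4); enrolment 207 per arm with 20% loss (Section 12.1.1.2); 165 per arm expected at 36 months (Section 8.1); five strata with weights n_j/n (Section 12.2.3). The documents do not give the arm split within strata, so that is an assumption below.

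**1. The plan's sample sizes.** With unpooled variance and no true difference, n per arm = 2p(1−p)(z₀.₉₇₅ + z₀.₉₀)²/Δ², where (1.960 + 1.2816)² = 10.507.

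- Office-based: 0.0392 × 10.507 / 0.0025 = 164.8 (plan: 165).
- Surgical: 0.0198 × 10.507 / 0.0016 = 130.03 (plan: 130).
- Enrolment: 165 / 0.8 = 206.25, rounded up to 207.

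The sizes reproduce. A one-sided 0.05 would give 135 and 106, so 0.025 is one-sided and corresponds to a two-sided 95% interval.

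**2. How the interval fails.** Take 3 mesh events and 0 control events among 165 per arm, unstratified, margin 4%. D = 3/165 = 0.01818 and V = 0.01818 × 0.98182/165 + 0 = 0.0001082. The upper limit is 0.01818 + 1.96 × 0.01040 = 0.0386, below 0.04, so non-inferiority is declared. A score test uses the variance under the null. Here the restricted estimates are 4% and 0%, the variance is 0.04 × 0.96/165 = 0.0002327, and Z = (0.01818 − 0.04)/0.01526 = −1.43, well short of −1.96.

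**3. Error at the null boundary.** Non-inferiority is declared if D + 1.96√V < Δ. True rates are 5% vs 1% (surgical) and 7% vs 2% (office-based). Nominal error is 2.5%.

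| | Surgical | Office-based |
|---|---|---|
| Exact, unstratified, 165 per arm | 4.6% | 4.1% |
| Exact, unstratified, 207 per arm | 4.9% | 3.6% |
| Exact, every n from 165 to 207: range (mean) | 4.0–5.5% (4.7%) | 3.5–4.2% (3.8%) |
| Five balanced strata, simulated, 165 per arm | 4.7% | 4.1% |
| Five balanced strata, simulated, 207 per arm | 4.8–4.9% | 3.6–3.7% |

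The ratios run from 3.5/2.5 = 1.4 to 5.5/2.5 = 2.2. Stratified and unstratified results agree closely, so the cause is the form of the interval and not the stratification.

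**4. Sensitivities.**

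- Control rate 4%: about 3.1–3.2% for both tests.
- Arms unequal within strata, 165 per arm (assumed): outer strata near 30:70 give 5.7% (surgical) and about 4.4–4.5% (office-based); near 20:80 they give about 7.0% and 5.2%.
- If the 90% level of the primary safety test were carried over: 7.2–9.1% (surgical) and about 6.6–6.7% (office-based).
- Co-primary safety, 24% vs 14%, margin 10%, 90% interval: 5.2% unstratified and 5.3% stratified, against 5%.

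**5. A score limit instead.** Stratified Miettinen-Nurminen, same strata and weights, two-sided 95%, balanced strata:

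| | Surgical | Office-based |
|---|---|---|
| Error, 165 to 207 per arm | 1.7–1.9% | 2.1–2.2% |
| Power, 207 per arm | 87% | 87% |
| Power, 165 per arm | 76% | 77% |
| Power, 130 per arm (stated surgical size) | 59% | – |

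Part of the loss is the score limit's own conservatism. A normal-approximation test recalibrated to 2.5% (at 207 per arm, critical value 2.25 for surgical and 2.13 for office-based) has about 94% and 92% power at 207 per arm, 84% for both at 165, and 71% for surgical at 130.

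**The case against.** The strongest reply concedes the arithmetic and disputes its weight.

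- **The top of the range is a peak.** The 5.5% occurs at n = 171, and only 5 of the 43 sample sizes from 165 to 207 exceed 5.25% for the surgical test. This is fair: the mean of 4.7%, or 1.9 times nominal, describes that test better.
- **The rates are only approximate.** At a 2% control rate the surgical error is already down to about 3.5–3.8% at 165 and 207 per arm. This too is fair, but 1% and 2% are the plan's own planning values.
- **The level can be inferred.** Primary safety is sized at 0.05 and tested with a 90% interval, so 0.025 points to 95%. That is the natural reading, and the missing level alone would be only a clarification. The 90% figures show what the gap would cost if read otherwise.
- **The denominator is partly covered.** Section 12.2.1 puts primary and secondary endpoints on ITT, and the sixth secondary endpoint concerns re-intervention. Sections 12.3.3 and 12.3.4 do not say that this applies to them.
- **The score limit errs on the safe side of nominal, and the study does not plan to analyse 130 per arm.** Both are true. At 207 per arm the power cost is small.
- **These are additional analyses.** They are, and this limits the severity. It does not make the stated error level correct.

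**Conclusion.** The concern holds. As written, the two tests do not deliver the 2.5% error at which they were sized. At the anticipated control rates, with a two-sided 95% interval and balanced strata, actual error averages about 4.7% for surgical and 3.8% for office-based intervention over 165 to 207 per arm, with extremes of 3.5% and 5.5%. The inflation shrinks if control rates are higher than anticipated. It grows if the arms are unequal within strata, which is plausible because centers are intended mainly to enroll one arm (Sections 8.2 and 12.2.2). The co-primary safety conclusion is not materially affected. This should be corrected before analysis, but it does not undermine the main result.

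**What to change.** For Sections 12.3.3 and 12.3.4 only:

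1. Keep the five strata and the n_j/n weights, and replace the normal-approximation limit with a stratified Miettinen-Nurminen score limit.
2. State the confidence level. Two-sided 95% matches the sizing level of 0.025.
3. State the denominator: ITT, or subjects with 36-month data.
4. Restate the power of both tests under that method and denominator.

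If a stratified Newcombe limit is preferred, its form must be specified. Wilson limits on the weighted arm proportions with an effective sample size give 1.8–2.2% error at 165 to 207 per arm. Averaging Wilson limits computed stratum by stratum is far too conservative here: for the surgical test at 165 per arm, error is 0.7% and power 34%.

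The cost is a change of wording for two tests and a little programming of a standard method. Data collection, strata and co-primary analyses stay as they are. The stated power becomes slightly less favourable at 207 per arm and clearly less so at 165 or 130.

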7.1. Primary Endpoints

The primary endpoint of the study is to achieve superiority of mesh over native tissue repair at 36 months as compared to baseline.

Success will be based on a composite of objective and subjective measures, and subjects will be considered a surgical success if each of the three criteria is met:

1. Objective success is achieved by the subject having an anatomic outcome defined as the leading edge of prolapse at or above the hymen in the operated compartment:
 - Anterior segment: Leading edge of anterior prolapse is at or above the hymen or POP-Q point Ba \leq 0.

- Apical segment: The vaginal apex does not descend more than one-half into the vaginal canal (i.e. POP-Q point C < -1/2 TVL) for multi-compartment prolapse or POPQ point C ≤ 0 for single compartment apical prolapse.
2. Subjective success is achieved if the patient denies symptoms of vaginal bulging per PFDI-20 question 3, answering “no” or “yes” but “Not at all” bothersome (<2).
 3. No retreatment for POP: no additional surgical treatment for POP in the segment(s) of the vagina treated at the index surgery or no pessary use since index surgery (i.e., ‘treated segment’ refer to the target compartment).

Additionally, a co-primary endpoint of the study is to achieve non-inferiority of mesh to native tissue repair for safety by comparing rates of serious device or serious procedure complications between baseline and the 36 month time point. Serious injury is defined per 21 CFR 803.3, i.e., life threatening, results in permanent impairment of a body function or permanent damage to a body structure, or injury or illness that requires medical or surgical intervention to preclude impairment of a body function or permanent damage to a body structure.

7.2. *Secondary Endpoints*

The secondary endpoints of the study include assessments of complications and subject reported outcomes:

1. Incidence of mesh erosion
2. Incidence of mesh exposure
3. Incidence of de novo dyspareunia
4. Improvement in subject-related outcomes at 36 months compared to Baseline ((pelvic floor symptoms (PFDI-20), QOL (PFIQ-7), sexual functioning (PISQ-12) TOMUS pain scale)
5. Assessment of subject’s level of improvement, measured by the Patient Global Impression of Improvement for Prolapse (PGI-I for Prolapse)
6. Absence of re-intervention and re-surgery for recurrence of POP, persistence of disease, or mesh exposure/erosion
7. Surgical success based on the following composite outcome:

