11.4.7. Months 6, 12, 18, 24, 36 Visits (-4/+12 weeks)

- Pelvic exam with vaginal length measurement
- Assessment of infection (vaginal, bladder)
- Prolapse grading (POP-Q Scoring)
- Assessment of pain (TOMUS pain scale) and analgesic intake
- PFDI-20
- PFIQ-7
- PISQ-12

- PGI-I for Prolapse
- SSQ-8 for surgical satisfaction (Months 6, 12, 24, 36 only)
- EQ-5D for health status (Months 12, 24, 36 only)
- Assessment of adverse events (device, procedure, or pelvic floor related)
- Assessment of risk factors
- Study completion (Month 36 only)

All subjects who have completed the study surgery and discharge will proceed to be followed through the above-outlined study visits to Month 36 where the primary endpoint analysis will be achieved when the last subject completes this visit. All subjects completing the Month 36 visit will be considered to have completed the study.

11.5. *Re-Intervention/Re-Surgery*

It is the intention of this study to demonstrate an improvement in anterior/apical pelvic organ prolapse through clinical effectiveness of a transvaginal prolapse repair kit. However, it is recognized that during the course of the study, there is a possibility subjects may require a medical re-intervention for events including but not limited to failed prolapse repair, persistence of prolapse symptoms, or a mesh or procedure-related complication. A re-intervention may include surgical or non-surgical treatments and can occur for a medical complication or for prolapse recurrence. For the purpose of this study surgical interventions shall be classified as “re-surgery” and non-surgical interventions shall be classified as “re-interventions”. Analyses will be performed to compare the rate of office-based interventions and of surgical interventions for medical complications and for prolapse recurrence in both treatment groups.

Non-surgical interventions (re-interventions) are defined as office-based procedures and do not involve an operating room procedure. Examples of non-surgical interventions may include but are not limited to an office visit to trim exposed mesh or suture in the vagina, a pessary, or physical therapy to treat procedural complications or persistent prolapse symptoms. Data on non-surgical interventions will be captured in the CRFs. Subjects will continue to be followed per the regular study visit schedule.

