Surgical interventions (re-surgery) are surgical operations performed to correct recurring prolapse symptoms, a procedural complication, or a mesh-related complication. These surgical events typically may occur on an outpatient basis yet can require admission to a hospital. The decision to perform a re-surgery for failed prolapse repair or persistence of prolapse symptoms will be per physician and subject discretion and all re-surgery data will be captured in the Case Report Forms. All subjects defined as having a prolapse recurrence will be those who have anatomic and symptomatic failure of their prolapse surgery (prolapse beyond the hymen and symptoms of vaginal bulge).

Subjects undergoing a re-surgery will be followed to 36 months post their initial study procedure as indicated in Table 10.1-2. The subject should return to the clinic for the next regular study visit as per her original schedule. If the subject elects to not undergo re-

surgery, then the subject will be followed to the Month 36 visit unless the subject chooses to withdraw consent from the study. No subject will be followed for more than 36 months beyond their initial study procedure.

11.6. *Subject Death*

If any serious adverse event results in death (regardless of the relatedness to the study device, procedure, or pelvic floor), the event is to be documented in the source documentation, Case Report Form, and reported to the Sponsor within the timeframe noted in Table 21.7-1 (Investigator Reporting Requirements). If an autopsy is conducted, a copy of the final autopsy report should be submitted to the Sponsor or designee. The primary objective of the autopsy is to determine the cause of death, complications and other relevant findings.

12. Statistical Considerations

12.1. *Endpoints*

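### The within-arm logistic model in section 12.3.4 uses a covariate that partly duplicates the endpoint's retreatment criterion, so its coefficient is partly definitional and separation is a risk

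*Combined protocol and SAP*

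**What the plan says.** - **The model.** Section 12.3.4: "For each group, logistic regression will be performed", "to include office-based intervention for recurrence as a covariate for analyzing the primary endpoint". The sentence glosses that endpoint as success in prolapse improvement at 36 months.
- **The endpoint.** Section 7.1, repeated in the synopsis: "subjects will be considered a surgical success if each of the three criteria is met". The third criterion, labelled as absence of retreatment, reads "no additional surgical treatment for POP in the segment(s) of the vagina treated at the index surgery or no pessary use since index surgery".
- **The covariate.** Section 11.5 defines non-surgical interventions as office-based procedures. It introduces its list with "Examples of non-surgical interventions may include but are not limited to", then names trimming of exposed mesh or suture, "a pessary, or physical therapy to treat procedural complications or persistent prolapse symptoms".
- **Recurrence.** Section 11.5 counts as recurrences "those who have anatomic and symptomatic failure of their prolapse surgery". It attaches no time point to this.
- **Separation.** The plan does not say what will be done if the covariate perfectly predicts failure in an arm.

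**The concern.** A predictor should not be part of the definition of the outcome. Here a woman who receives a pessary for recurrence is in the exposed group and, through criterion 3, is also a failure. Because the criterion runs from the index surgery onward, a good anatomic and symptomatic result at Month 36 cannot reverse this. For these women the regression returns the endpoint definition.

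Two consequences follow. When the model fits, its coefficient mixes a definitional part with any real association, and nothing in the output shows the mixture. When no exposed woman in an arm is a success, the term has no finite maximum-likelihood estimate, and the software will print a very large odds ratio and standard error. In either case a reader could take the result as evidence about how women fare after office-based treatment.

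**Working it through.** **Inputs.** The plan states no figure for this model, so there is none to reproduce. From the documents: success "assumed to be 70.0% for the native tissue arm and 85.0% for transvaginal mesh arm" (section 12.1.1.2) and 165 evaluable women per arm (section 8.1). This gives 0.70 × 165 = 115.5, taken as 116 successes and 49 failures with native tissue, and 0.85 × 165 = 140.25, taken as 140 and 25 with mesh. Not in the documents, and therefore assumed: the number of exposed women in an arm, k; the share treated without a pessary, s; and the success rate in that share, q. Complete outcome data are assumed.

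**Step 1: no exposed successes.** Native tissue arm, k = 8, all failures: exposed 0 successes and 8 failures, unexposed 116 and 41. The intercept is ln(116/41) = 1.040 (SE 0.18). The covariate term does not settle under Newton iteration:

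| Iteration | Coefficient | SE |
|---|---|---|
| 5 | −7.2 | 7.9 |
| 12 | −14.2 | 260 |
| 25 | −27.2 | about 173,000 |

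The log-likelihood levels off at −90.158. This is quasi-complete separation: only the one coefficient and its SE diverge. The mesh arm with k = 4, all failures, behaves in the same way.

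**Step 2: one exposed success.**
- Native tissue, k = 8: exposed 1 and 7, unexposed 115 and 42. Log OR = ln[(1 × 42)/(7 × 115)] = −2.95. SE = √(1 + 1/7 + 1/115 + 1/42) = 1.08.
- Mesh, k = 4: exposed 1 and 3, unexposed 139 and 22. Log OR = ln[(1 × 22)/(3 × 139)] = −2.94. SE = √(1 + 1/3 + 1/139 + 1/22) = 1.18.

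Both are ordinary finite fits.

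**Step 3: what a finite fit contains.** Suppose that in the native tissue case 6 of the 8 had a pessary and, of the other 2, one succeeded. Those 2 alone against the unexposed give ln[(1/1)/(115/42)] = −1.01. The model reports −2.95. The difference, ln 7 = 1.95, comes entirely from the 6 women who are failures by definition.

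**Step 4: chance of separation.** With pessary users always failures and women independent, P(no exposed success) = (1 − s·q)^k.

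| s | q | k = 2 | k = 4 | k = 8 | k = 16 |
|---|---|---|---|---|---|
| 0 | any | 100% | 100% | 100% | 100% |
| 0.25 | 0.25 | 88% | 77% | 60% | 36% |
| 0.25 | 0.5 | 77% | 59% | 34% | 12% |
| 0.25 | 0.7 | 68% | 46% | 21% | 5% |
| 0.5 | 0.5 | 56% | 32% | 10% | 1% |
| 0.75 | 0.5 | 39% | 15% | 2% | under 1% |

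For example, s = 0.25 and q = 0.5 give 0.875^8 = 0.34. If an arm has no such interventions, the term is not estimable at all.

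**The case against.** A reader might infer that the model is tautological and cannot converge. The documents do not support that. The covariate is any office-based intervention for recurrence, from an open list that also names physical therapy, which is not a failure criterion. Recurrence carries no time point while success is judged at 36 months, so a woman treated earlier without a pessary can still be a success. One such woman gives a finite fit (step 2). A simulation that fixes exposed successes at zero would show what separation does, not how likely it is.

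Three further objections deserve an answer.

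- **The *or* in criterion 3.** Read literally, a pessary user without repeat surgery meets the criterion and the definitional link disappears. But the same reading would pass a woman with repeat prolapse surgery and no pessary, under a criterion labelled as absence of retreatment. The workable reading is neither surgery nor pessary. The point depends on it.
- **The outcome may not be the composite.** Sections 12.3.4 and 12.1.1 speak loosely of improvement in prolapse. The hypotheses and sample size for the primary endpoint use composite success, so the composite is the likely meaning, though the text could be clearer.
- **Little depends on this model.** This stands. It has no stated hypothesis, margin or decision rule. Section 12.3.5.2 already compares women with and without office-based intervention on quality of life and adverse events, which criterion 3 does not define.

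**Conclusion.** The point holds in limited form, and its severity is minor. The covariate partly duplicates the retreatment criterion, so its coefficient cannot be read as an effect of office-based treatment or as a genuine predictor, whether or not the fit converges. The convergent case is the more troublesome, because no warning accompanies it.

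Quasi-complete separation is a real risk of unknown size: across the assumptions in the table it runs from under 1% to 100%. All of this rests on criterion 3 meaning neither repeat surgery nor pessary, and on the outcome being the composite. The primary comparison, the propensity-stratified difference in proportions of sections 12.1.1.3 and 12.2.3, does not use this model and is unaffected.

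**What to change.** 1. In section 12.3.4, replace the composite in this sub-analysis with the Month 36 anatomic and bulge criteria, leaving out the retreatment component. Report them by office-based intervention for recurrence within each arm as a cross-tabulation.
2. If a model is kept, prespecify Firth or exact logistic regression to deal with separation.
3. Label the result descriptive. Section 11.5 defines recurrence by anatomic and symptomatic failure, so the covariate stays tied to the two remaining criteria. The change reduces the circularity but does not remove it.
4. Reword criterion 3 so that its *or* has one meaning, wherever the clause appears: the synopsis, sections 7.1 and 7.2, and section 12.1.2.

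The cost is wording only. POP-Q and PFDI-20 are already scheduled at Month 36 in Table 11.1-1, and section 11.5 already has non-surgical interventions captured on the case report forms. No new data, visits or subjects are needed.
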